Aim 1: Examine the feasibility and acceptability of the iBHE program among low-income cancer survivors living with co-morbid conditions. Eight participants who have completed treatment for a solid tumor cancer with at least one comorbidity (e.g., diabetes and/or hypertension) will be assigned to an open-label trial of the idea. We will gather feedback on goal setting, problem-solving strategies, exercise choices, and tracking mechanisms, program feasibility, and acceptability and modify the intervention as needed prior to Phase 2.

Phase 2:

Aim 2: pilot testing the effect of the tailored iHBE on fatigue, pain, affective well-being, resilience and BDNF level among low-income cancer survivors living with co-morbid

Date: November 14, 2018

Principal Investigator: [name]

Application Number: IRB00175781

conditions at completion (12 weeks) and 6 months in comparison to usual care waiting list group. After adjustment in the protocol based on Aim 1, 50 participants who meet the inclusion criteria will be randomly assigned to a 12-week experimental (preferred physical activities) group or a usual care usual care (waiting list) group. Variables will be measured at baseline, completion (12 weeks) and 6 months. *Hypothesis 2: After controlling for the age, gender, race, and BMI, participants in the experimental group will have a great decline in fatigue, pain, and a greater increase in AWB, resilience and BDNF level from baseline to program completion and 3 months compared to the usual care group.*

Aim 3: Examine the association between the changes in the biomarker (BDNF) in serum and sweat after the 12-weeks from baseline and at 3 months post program completion from baseline iBHE program. *Hypothesis 3: the change in the serum BDNF level is positively associated with a change in the sweat BDNF level at the after the 12-weeks from baseline and at 6 months from baseline iBHE program.*

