Aim 2: Pilot testing the effect of the tailored iHBE on fatigue, pain, affective well-being, resilience and BDNF level among low-income cancer survivors living with co-morbid conditions at completion (12 weeks) and 6 months in comparison to usual care waiting list group.

After adjustment in the protocol based on Aim 1, 50 participants who meet the inclusion criteria will be randomly assigned to a 12-week experimental (preferred physical activities) group or a usual care usual care (waiting list) group. Variables will be measured at baseline, completion (12 weeks) and 6 months.

Hypothesis 2: After controlling for the age, gender, race, and BMI, participants in the experimental group will have a greater decline in fatigue, pain, and a greater increase in AWB, resilience and BDNF level from baseline to program completion and 3 months compared to the usual care group.

Aim 3: Examine the association between the changes in the biomarker (BDNF) in serum and sweat after the 12-weeks from baseline and at 3 months post program completion from baseline iBHE program. Hypothesis 3: the change in the serum BDNF level is positively associated with a change in the sweat BDNF level at the after the 12-weeks from baseline and at 6 months from baseline iBHE program.

Sample and Setting:

The study participants will be recruited from the home health care agencies in Baltimore, Maryland, Johns Hopkins Comprehensive Cancer Center and Johns Hopkins Hospital.

Inclusion criteria are (1) participants diagnosed with solid tumor cancer who have completed cancer treatment at least 6 months; (2) diagnosed with diabetes and/or hypertension for at least a year; (3) aged 21 years or older, (4) have an annual household incomes of below \$30,000 for families of three, (5) the average fatigue level within the past 7 days at the level of 3 or more on the 0 (no fatigue) to 10 (worse fatigue) Likert scale and (6) give informed consent.

Exclusion criteria are those (1) currently undergoing treatment for cancer; (2) have an active infection (e.g., fever, localized redness, swelling, sinus congestion); and/or (3) diagnosed with a psychological disorder (e.g., suicidal or homicidal tendencies, extreme anxiety or depression).

Sample size justification

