Phase 2: With an alpha level of .05, the statistical power of 0.80, and 25 participants per group, we will be able to detect significant differences of moderate to large effect sizes of 0.65 when comparing change across baseline, 3-months, and 6-months between the two groups. With an attrition rate of 12% (22 participants per group), the detectable effect size increases to 0.69. Since this is a pilot study and not powered to detect small to moderate effect sizes, we will pay close attention to the effect size, rather than statistical significance. These effect size estimates will be used to inform future research trials.

Date: November 14, 2018

Principal Investigator: [name]

Application Number: IRB00175781

Randomization: Eligible participants will be randomized in a 1:1 allocation ratio to one of the two treatment arms. The electronic Research Electronic Data Capture (REDCap), a randomization application will be used to randomly assigned the participants to the groups

Data Collection Schedule and Procedures. Upon receiving approval from the Johns Hopkins University Institutional Review Board, the study flyer will be posted and distributed at the home health care agencies in Baltimore, Maryland, Johns Hopkins Comprehensive Cancer Center and Johns Hopkins Hospital.

Recruitment, Informed Consent, and Confidentiality. Recruitment methods for this study include (1) distributing and posting flyers, with a tear-off phone number to speak with the principal investigator (PI) as necessary, posted at the hospital (2) face-to-face recruitment for potential participants during cancer support group meetings; and (3) word-of-mouth. Potential participants will receive a verbal explanation by phone or face to face meeting in terms suited to their comprehension of the purpose, procedures, and potential risks of the study. During the screening for eligibility process, an oncologist will be available for consultation. The oncologist will be notified and consulted for the appropriateness of the exercise for participants who self-report having co-morbidities. The participants and family or legal guardian will have an opportunity to carefully review the consent form and ask questions regarding this study prior to signing. Participants will be encouraged to consult with their primary doctor if any concern or an additional question. Participants will be informed that they may withdraw from the study at any time without prejudice to themselves.

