Participants will be approached and screened for the annual income below \$30,000 for families of three, average fatigue level within the past 7 days at the level of 3 or more on the 0 (no fatigue) to 10 (worse fatigue) Likert scale, the self-report perceived ability to walk for six-minute and the exertion level after the walk on a 0-10 numeric perceived exertion scale (0 = no exertion at all to 10 = maximal exertion). Eligible participants will be asked if they would like to participate and to sign the informed consent. Participants will be asked to have the research team visit their home for the initial assessment and to provide instruction on the exercise, the physical activity tracker and how to complete the questionnaire via the phone application for 4 weeks, followed by phone follow up for 7 weeks. Participants will be asked to wear the FitBit Charge 2 on the non-dominant arm and respond to the phone application daily for 12 weeks. Participants' peripheral blood will be drawn at week 1 and week 12 by a registered nurse or certified phlebotomist. We will ask the participant to have a sweat pad placed on their upper abdomen or flank for 72 hours to collect the sweat at baseline (before the program) and week 12 (at the program completion).

At the end of the program, a research team member will visit participants' home and evaluate the participants' perception and satisfaction for the program using a open ended questionnaires. Participants will be asked to complete the questionnaires. Participants' blood and sweat will be collected.

Intervention/Independent Variables

Tailored Technology-Enhance Home-based Exercise Program:

The tailored technology enhanced home-based exercise (iHBE) program: Participants in this group will receive an adjusted (based on the feedback from phase 1)12-week program with 1 assessment home visit session, 5 home visits during exercise and 7 follow up phone calls. The technologies, a wearable device and a smartphone application, will be used as a tool to monitor physical performance (heart rate, step count), provide immediate feedback, send daily reminding message through mEMA. The coded raw data without personal identification information from the wearable device will be sent to the servers where we can store it in the database alongside the mEMA data and create custom reports showing HR 30 minute before each EMA survey, showing HR and previous self-report responses before/ after each automatically triggered

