Date: November 14, 2018

Principal Investigator: [name]

Application Number: IRB00175781

EMA.

Usual Care (Waiting List) Group: The usual care waiting list group will receive educational booklets about a healthy lifestyle and cancer survivorship. Participants will be asked to wear the wearable device during the waiting period to monitor the PA (steps and heart rate). They will receive a notification to rate their daily fatigue level for 3 months. Usual Care participants will receive the iHBE after the conclusion of the study (as described above).

Variables and measurements.

The study variables will be measured as follows:

Measure	Description	Psychometrics
NINR Common Data Elements (CDEs)	23-item; measure demographic and disease information data	
PROMIS Short Form V1.0-Fatigue 6a	6-items; self-reported fatigue (frequency, duration, intensity) and the impact to physical, mental, and social activities, has five response options (1 or never to 5 or always).	Initial psychometric properties have shown an internal consistency reliability coefficient of greater than 0.80. ⁵²
PROMIS Pain Intensity – Short Form 3a V1.0.	Universal and not disease-specific instrument for pain, 3-items (worst, average, and current pain) measure from 1 (no pain) to 5 (very severe).	Conceptually validated with established reliability Test-retest values = .83 to .93. (PROMIS, 2015)
Wrist worn wearable device: FitBit Charge 2	PA (steps count and Heart rate) tracking device (wrist worn)	Intraclass Correlation Coefficients with ActivPAL are 0.81 and 0.96 respectively, $p < .01$. (Kooiman et al., 2015)
Connor-Davidson Resilience Scale	10 item self-report rating scale 0 (not true at all) to 4 (true nearly all the time)	Good internal consistency (Cronbach's alpha 0.85) and constructs validity. (Campbell-Sills & Stein, 2007)
Short form survey (SF-36)	36 item self-report instrument measure 2 domains: physical well-being and affective well-being.	Good internal consistency for every scales (Cronbach's alpha ≥ 0.70). (Busija et al., 2011)

Serum and Sweat BDNF protein levels will be measured by the enzyme-linked immunosorbent assay (ELISA). Participants' peripheral blood will be drawn during home visits, the sweat patch will be placed on the participants' upper abdomen or flank for 72 hours to collect the sweat at baseline, 12 weeks and 3 months after the program completion. The ELISA will be performed according to manufacturer's guide by one laboratory technician.

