Exclusion criteria are those (1) currently undergoing treatment for cancer; (2) have an active infection (e.g., fever, localized redness, swelling, sinus congestion); and/or (3) diagnosed with a psychological disorder (e.g., suicidal or homicidal tendencies, extreme anxiety or depression).

6. Drugs/Substances/Devices

None

7. Study Statistics

Phase 2 Data analysis

To test **Hypothesis 2 (Aim 2)** examining the effectiveness of iHBE program on fatigue, pain, well-being, resilience and BDNF levels, generalized estimating equations (GEE) will be used. The models will include time as a within-subject fixed effect (baseline, 3 months, 6 months), group (intervention vs usual care) as a fixed-effect between-subject factor and the group by time interaction. Baseline age, race gender, and BMI will be included as covariates. A significant group by time interaction would signify that the change over time in the outcomes differed for the intervention and usual care groups. GEE was selected because it uses all available data and does not require complete data across time for a participant to be included in the analyses. Correlation will be used to test the relationship between the changes in serum and sweat BDNF levels (**Aim 3**). Change from baseline to 3 months and change from baseline to 6 months will be computed for serum BDNF and separately for sweat BDNF. The correlation between the change scores measured by the different modes will be estimated at each time point

8. Risks: Same as phase 1

9. Benefits: Same as phase 1

10. Payment and Remuneration

Date: November 14, 2018

Principal Investigator: [name]

Application Number: IRB00175781

Phase 2 (Aim 2 and 3) - The participants in both the intervention group and the control group will each receive a total of \$80 (\$20 at the start of the intervention, \$30 at the end of the intervention and \$30 at 6 months)

11. Costs

There will be no cost for participants to participate in this study.

12. Data Safety Monitoring Plan

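### The Phase 2 procedures list BDNF sampling at two times, but the aims and the analysis need a third, at 6 months

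*Combined protocol and SAP*

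**What the plan says.** All places are in the Phase 2 part of the combined protocol and SAP unless noted.

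- **Section 4, Recruitment, Informed Consent, and Confidentiality.** For blood: "peripheral blood will be drawn at week 1 and week 12 by a registered nurse or certified phlebotomist". For sweat, a 72-hour patch is used to "collect the sweat at baseline (before the program) and week 12 (at the program completion". A later sentence on taking blood and sweat refers to the end of the program, which is the same week-12 occasion.
- **Phase 2 Specific Aims (also section 2, Objectives).** Aim 2 names BDNF as an outcome and states: "Variables will be measured at baseline, completion (12 weeks) and 6 months". Hypothesis 3 concerns serum and sweat BDNF change after 12 weeks and "at 6 months from baseline iBHE program".
- **Section 4, Variables and measurements.** The patch is used to "collect the sweat at baseline, 12 weeks and 3 months after the program completion". Blood is said only to be taken at home visits.
- **Section 4, Data Collection Schedule and Procedures.** Blood belongs to the baseline assessment, before the 7-day wear period and randomization. A 6-month home visit follows the list of iHBE-group visits, with no samples named.
- **Section 7, Study Statistics.** For Aim 2: "The models will include time as a within-subject fixed effect (baseline, 3 months, 6 months". For Aim 3, on the scores to be correlated: "Change from baseline to 3 months and change from baseline to 6 months will be computed for serum BDNF and separately for sweat BDNF".

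On the waiting-list arm, the description of the usual care group offers iHBE once the study has ended. The Data Collection Schedule offers it once the 12-week program has ended.

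**The concern.** The recruitment and procedures text is the only Phase 2 text that ties the blood draws explicitly to week numbers, and Phase 2 has no visit table like the one in Phase 1. A coordinator could reasonably work from that text and take no BDNF sample after week 12. The 6-month Aim 3 correlation and the 6-month BDNF part of Aim 2 would then be empty. Samples not taken cannot be obtained afterwards. The plan chose GEE because it uses all available data, but that does not help when a time point is absent for every participant.

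There is a smaller labelling problem. The first draw is put at week 1, while the matching sweat sample is put at baseline. Aim 3 correlates changes from baseline in the two media, so both should start from the same defined occasion.

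The waiting-list statements matter for the same 6-month time point. On one reading the controls are still untreated at 6 months; on the other they may already have been through the program.

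**Working it through.** **1. Sampling times side by side**

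| Place (Phase 2) | Serum | Sweat | 6 months included? |
|---|---|---|---|
| Section 4, Recruitment text | week 1, week 12 | baseline, week 12 | No |
| Aim 2 (BDNF, medium not named) | baseline, 12 weeks, 6 months | same | Yes |
| Hypothesis 3 | change at 12 weeks and 6 months | same | Yes |
| Section 4, Variables and measurements | home visits; the time list can be read as covering blood | baseline, 12 weeks, 3 months after completion | Yes for sweat, implied for serum |
| Section 7, Aim 3 | change to 3 and 6 months | same | Yes |

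The longer lists agree with one another: the documents treat 12 weeks as 3 months, so 3 months after completion is 6 months from baseline. Only the recruitment text stops at week 12.

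**2. Likely source.** The Phase 1 recruitment text has the same blood sentence with week 4 in place of week 12. In Phase 1 the first draw is also labelled week 1, although the Phase 1 data collection table puts it at Week 0. Both features suggest carried-over text, and that week 1 means baseline.

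**3. The plan's own attrition figure.** The sample size justification states: "With an attrition rate of 12% (22 participants per group), the detectable effect size increases to 0.69". The retained number reproduces: 25 × (1 − 0.12) = 22 per group, 44 in total.

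**4. Sample counts**

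- Needed by the analysis: 3 times × 2 sample types × 50 = 300.
- Listed in the recruitment text: 2 × 2 × 50 = 200.
- Gap: 300 − 200 = 100 (50 serum, 50 sweat), all at 6 months.
- With 44 retained: 44 × 2 = 88, assuming all attrition has occurred by 6 months.

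Analyses left without data: 1 of 2 Aim 3 correlations, and 1 of 2 follow-up times in the Aim 2 BDNF model.

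**5. Link to the stated detectable effects.** The plan gives 0.65 with 25 per group and 0.69 with 22, for change across three times. A plain two-sided two-group comparison gives (1.960 + 0.842) × √(2/25) = 0.79 and, with 22, 0.85. Multiplying by √((1 + (m − 1)ρ)/m) with m = 3 times and ρ = 0.5 gives 0.647 and 0.690, which match. The plan states neither this formula nor ρ; with 25 per group, ρ from 0.3 to 0.7 gives 0.58 to 0.71. The formula describes an average over occasions rather than a group-by-time interaction, so it serves only as a guide. On that basis, with ρ = 0.5, two times instead of three would move the BDNF figures to about 0.69 and 0.73. The inconsistency does not depend on this step.

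**6. Waiting-list timing.** Suppose the controls begin iHBE straight after week 12 (an assumption). A 12-week program then ends at 12 + 12 = week 24. Six months is week 24 if 12 weeks counts as 3 months, or week 26 by calendar. They could therefore have completed the whole program by the 6-month measurement.

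**The case against.** The best defence is that the recruitment text is silent after week 12 rather than forbidding a later sample. It describes participation up to the end of the program and mentions no 6-month activity at all, not even the questionnaires that Aim 2 plainly requires. Elsewhere there is a 6-month home visit, blood is to be taken at home visits, and both arms are paid at 6 months. Read together, these make the intended schedule recoverable. That is fair, and the loss of data is conditional on staff following the one text. But no sentence places samples at the 6-month visit, and that visit is described after the iHBE-group contacts, so 6-month collection in the control arm is not described.

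The three-time list under Variables and measurements attaches grammatically to sweat. This stands: a 6-month blood draw is implied there, not stated. Section 7 nevertheless needs 6-month serum values explicitly.

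The counts assume that all 50 participants give both sample types. Aim 2 does not name the medium, and Aim 3 could be read as confined to the iHBE arm. If sweat were needed only in that arm and serum in both, the 6-month gap would be 50 + 25 = 75 samples. It would still be the whole time point.

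Hypothesis 2 refers to completion and 3 months, without naming 6 months. Read as 3 months from baseline, this would simply repeat completion, so 3 months after completion is the sensible reading and agrees with Aim 3.

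The waiting-list question is a separate issue, and the end of the study could be meant as the end of the 12-week period. It is an ambiguity that needs settling, and the sampling point does not rest on it. Finally, Phase 1 states that Phase 2 will be submitted later and may be adjusted. That makes correction easy but does not make the present text consistent.

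**Conclusion.** The inconsistency is real. The recruitment and procedures text gives two of the three BDNF sampling times that the aims and section 7 require, and it omits 6 months for both serum and sweat. Followed literally, it leaves 100 of 300 samples untaken at full enrolment, or 88 six-month samples after the stated attrition. It removes all data for the 6-month Aim 3 correlation and for the 6-month BDNF level in Aim 2. The counts assume both sample types from all participants in both arms. The cause is probably an incomplete edit, and the intended schedule can be inferred, so this should be corrected but is not a flaw in the design itself. The week 1 label is minor. The waiting-list wording needs reconciling because it changes the meaning of any 6-month between-arm contrast. The week-24 figure assumes that controls start immediately after week 12.

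**What to change.** Correct the Phase 2 recruitment and procedures text to agree with the aims, Variables and measurements, and section 7. Add one Phase 2 schedule table, modelled on the Phase 1 data collection table, that lists paired serum and sweat BDNF at baseline (before the program, replacing week 1), 12 weeks and 6 months for both arms. State that the 6-month visit applies to both arms and includes these samples. Reconcile the two statements on when the waiting-list arm receives iHBE, and say in section 7 what the 6-month between-arm comparison then estimates.

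The cost is wording and one table. Relative to the recruitment text it means one more blood draw and one more sweat patch per participant: 100 samples at full enrolment, or 88 after attrition. Aims 2 and 3 already require these samples, and section 10 already pays both arms at 6 months.

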Data Collection Schedule and Procedures:

Phase two is a pilot testing of the adjusted iHBE program effectiveness on the symptoms (fatigue and pain) affective well-being, resilience and BDNF level. A randomized usual care (waiting list) trial phase will be used. The study flyers will be posted at the home health care agencies, Johns Hopkins Comprehensive Cancer Center and Johns Hopkins Hospital. Eligible participants will be contacted by the principal investigator or research assistant who will explain the purpose of the study and requirements, and provided the study information and consent form. After providing the signed consent form, participants will complete the baseline assessment including the questionnaire, physical function (FTSST and 6MWT)

Date: November 14, 2018

Principal Investigator: [name]

Application Number: IRB00175781

and blood samples. A pre-installed application smartphone and a wrist-worn wearable device (FitBit Charge 2) will be loaned to the participants. The online account specific to the participant will be assigned using code. No personal information will be stored separately. Participants will be asked to wear the FitBit Charge 2 on the non-dominant arm and respond to the mEMA application to monitor their free-living PA level for 7 days then randomly assigned to the experiment and usual care waiting list group. Participants in the iHBE group will receive one assessment home visit, 5 home visits and 7 follow up phone calls during the iHBE program. Then a home follows up visit at 6 month. The usual care (waiting list) group will receive educational booklets about a healthy lifestyle. They will be asked to continue to wear the wearable device to monitor PA for 3 months. Participants will then receive the iHBE program after the conclusion of the 12-week program.

5. Inclusion/Exclusion Criteria

Inclusion criteria are (1) participants diagnosed with solid tumor cancer who have completed cancer treatment at least 6 months; (2) diagnosed with diabetes and/or hypertension for at least a year; (3) aged 21 years or older, (4) have an annual household incomes of below \$30,000 for families of three, (5) the average fatigue level within the past 7 days at the level of 3 or more on the 0 (no fatigue) to 10 (worse fatigue) Likert scale and (6) give informed consent.

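### The plan gives two times for the waiting-list arm to receive iHBE, and the earlier one would remove the usual-care comparator at 6 months

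*Combined protocol and SAP*

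**What the plan says.** Two places in Phase 2, section 4 (Study Procedures) say when controls get the program.

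- Usual Care (Waiting List) Group: "Usual Care participants will receive the iHBE after the conclusion of the study (as described above"). The same paragraph says of daily ratings, "They will receive a notification to rate their daily fatigue level for 3 months".
- Data Collection Schedule and Procedures (the one after the measures table): "They will be asked to continue to wear the wearable device to monitor PA for 3 months", and then "Participants will then receive the iHBE program after the conclusion of the 12-week program". This section mentions a 6-month home visit when it describes the iHBE arm, but not when it describes the controls.

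Elsewhere the plan treats 6 months as a randomised comparison with untreated controls.

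- Aim 2 (Phase 2 Specific Aims) tests the effect "at completion (12 weeks) and 6 months in comparison to usual care waiting list group".
- Section 7, Study Statistics, specifies a GEE with "time as a within-subject fixed effect (baseline, 3 months, 6 months), group (intervention vs usual care) as a fixed-effect between-subject factor" and their interaction. It adds: "A significant group by time interaction would signify that the change over time in the outcomes differed for the intervention and usual care groups".
- Section 10, Payment and Remuneration: "The participants in both the intervention group and the control group will each receive a total of" $80, of which $30 falls due at 6 months.
- The sample size justification says that attention will go to effect sizes more than to significance, and that the estimates will feed into later trials.

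**The concern.** The two instructions differ, and no other text reconciles them. The study does not end at 12 weeks, so the end of the program and the end of the study are different dates, about three months apart. The 6-month outcome falls at the end of that interval.

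If staff follow the schedule section promptly, controls will have just finished iHBE at the 6-month visit, while the intervention arm will be about three months past completion. The analysis would still label the groups as intervention and usual care. To the extent that controls benefit, the 6-month effect size shrinks. It could change sign if the intervention arm's gain has partly faded. No analysis of these data restores an untreated comparator once controls have been treated, and the effect size is the quantity this pilot means to carry forward. The group-by-time test also becomes hard to read, because a significant result could arise from controls catching up.

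**Working it through.** **1. Timeline.** Take 6 months as about 26 weeks and the program as 12 weeks. Weeks of iHBE received by controls at the 6-month visit = min(12, 26 − start week).

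- Schedule section followed promptly: a start at week 12, 13 or 14 gives 12 weeks in each case, so the full program is complete by week 24, 25 or 26. The start week is an inference, since the text gives no date.
- Usual Care paragraph followed: the start is at about week 26, so controls have received 0 weeks at the 6-month visit and finish at about week 38.

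The baseline-to-12-week contrast is the same under both.

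**2. The plan's own figures.** The stated detectable effects are 0.65 (25 per arm) and 0.69 (22 per arm, from 25 × 0.88 = 22), at alpha 0.05 and power 0.80. They reproduce as the average of three measurements with an assumed correlation ρ = 0.5, which the plan does not state:

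- 2.8016 × √(2/25) × √((1 + 2 × 0.5)/3) = 0.647
- 2.8016 × √(2/22) × √((1 + 2 × 0.5)/3) = 0.690

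These figures do not decide the timing question. Below, 0.65 serves only as a unit for illustration; it is a detectable effect, not an expected one.

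**3. What the 6-month contrast would show.** Let r be the share of the 12-week effect still present in the intervention arm and g the share gained by controls. Contrast = 0.65 × (r − g).

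| r | True effect against usual care | g = 25% | g = 50% | g = 100% |
|---|---|---|---|---|
| 1 | 0.65 | 0.49 | 0.325 | 0 |
| 0.5 | 0.325 | 0.16 | 0 | −0.325 |

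The documents give neither r nor g.

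**4. The group-by-time test.** Assume compound symmetry, unit SD, n = 25 per arm and arm differences δ = (0, 0.65, x) at baseline, 3 and 6 months. The 2-df chi-square noncentrality is (n/2) × Σ(δ − mean δ)² / (1 − ρ). For x = 0.65 and ρ = 0.5 this is 12.5 × 0.2817 / 0.5 = 7.04.

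| x at 6 months | Noncentrality, ρ = 0.5 | Power, ρ = 0.3 | Power, ρ = 0.5 | Power, ρ = 0.7 |
|---|---|---|---|---|
| 0.65 | 7.04 | 51% | 66% | 88% |
| 0.4875 | 5.72 | 42% | 56% | 80% |
| 0.325 | 5.28 | 39% | 53% | 76% |
| 0 | 7.04 | 51% | 66% | 88% |
| −0.325 | 12.32 | 76% | 89% | 99% |

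The rows for 0.65 and 0 are identical. The test is equally likely to be significant when the benefit is fully sustained against untreated controls and when treated controls have fully caught up.

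**5. Precision, for scale.** The 95% half-width for the 6-month change contrast is 1.96 × √(2/25 × 2 × (1 − 0.5)) = 0.55 SD.

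**6. Detectable 12-week change contrast (needed only for the fallback).** The formula is 2.8016 × √(2/n) × √(2(1 − ρ)), two-sided 0.05, 80% power.

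| n per arm | ρ = 0.3 | ρ = 0.5 | ρ = 0.7 |
|---|---|---|---|
| 25 | 0.94 | 0.79 | 0.61 |
| 22 | 1.00 | 0.84 | 0.65 |

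Adjusting for the baseline outcome, with √(1 − ρ²) in place of the last factor, would give 0.69 and 0.73 at ρ = 0.5. The planned model does not specify that adjustment.

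**The case against.** The strongest reply is that the harm is conditional. Most of the plan fits the later timing: Aim 2, the group label in the GEE, the 6-month payments and the Usual Care paragraph. The schedule sentence gives no start date and could be read as setting only an earliest time. That is fair, and if the later timing governs there is no bias. But the sentence follows three months of monitoring and says the program comes next, so prompt crossover is its natural reading. A text that permits starts on either side of an outcome visit also lets start times differ between participants. Reading the end of the study as week 12 would make the two places agree, but on the timing that spoils the comparison, and against the 6-month outcomes and payments.

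It can also be said that this is a small pilot and that the 12-week contrast survives. Both are true, but the pilot's stated product is effect sizes, and the 6-month one is among them.

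The numerical illustrations rest on assumed retention, control gain and correlation, and the power values do not move in one direction. They show that the test cannot be interpreted, not how large the bias would be. That the interaction test has 66% power rather than 80% at a sustained 0.65 (ρ = 0.5) is true without any crossover and is a separate matter.

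Finally, the 3-month limits on control monitoring sit awkwardly with a 6-month wait. They can stay: they match the iHBE arm's 12 weeks of device wear, and no 6-month outcome depends on them.

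**Conclusion.** The concern holds. The plan states two incompatible times for the waiting-list arm to receive iHBE, and only the later one fits Aim 2 and the analysis. If the earlier one is followed with a start at about weeks 12 to 14, controls will have completed the program by the 6-month visit, and the contrast no longer estimates iHBE against usual care. The textual conflict is certain. The bias depends on which instruction is followed, on how promptly, and on how much controls gain, so its size is not derivable from the documents. The consequence is confined to the 6-month comparison and its part of the group-by-time test. The conflict must be settled before any control reaches week 12, because the untreated comparator cannot be recreated afterwards.

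**What to change.** Replace the schedule sentence with, for example: *Waiting-list participants will complete the 6-month assessment and then receive the iHBE program.* The analysis plan does not change, and the timing correction does not require new sample size figures.

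**Cost.** There are no extra participants or assessments. Compared with the earlier timing, controls may wait about 12 to 14 weeks longer, so some may drop out before 6 months. Their home visits, calls and loaned devices must be available to about week 38 instead of about weeks 24 to 26. Compared with the Usual Care paragraph there is no added cost, because it already plans this.

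**Fallback, only if crossover at 12 weeks is intended.** Make baseline to 12 weeks the only between-arm test of Hypothesis 2, and label the 6-month data as immediate versus delayed iHBE. Correct the Usual Care paragraph, and restate the detectable effect for the 12-week change contrast (about 0.79 at 25 per arm and 0.84 at 22 per arm, assuming ρ = 0.5). This means rewriting Aim 2, Hypothesis 2, the analysis section and the sample size text, and it gives up the randomised 6-month comparison with usual care.
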